		1.1. Revision Date(s) add rows as needed	

Study Title: Examining the individual response to a restricted sodium diet in hypertensive patients

2. Background

Briefly discuss the important literature relevant to the trial and that provides background for the trial. Include the importance of the trial and any relevant treatment issues or controversies.

Excessive dietary sodium intake is an independent risk factor of hypertension and cardiovascular disease. A vast array of efforts have tried to reduce sodium consumption based on evidence indicating a public health benefit. Yet this benefit has been questioned, mainly based on studies showing variability in individual responses to a sodium-restricted diet (SRD).

The original Sodium Watchers Program (R01NR012967) was developed and implemented by [name] (University of Kentucky). In this pilot study, the modified Sodium Watchers Program will propose improving adherence to an SRD through education and digital self-monitoring for gradual reduction to low salt foods.

This variability may result from a range of factors, from genetics and lifestyle to various environmental parameters. The response of BP regulation to dietary interventions has been investigated through a metabolomics approach in several studies where different dietary patterns were adopted, including the Dietary Approaches to Stop Hypertension (DASH), Optimal Macronutrient Intake Trial for Heart Health Diets, and use of the Mediterranean Diet. BP was significantly associated with 6-10 urinary metabolites reflecting dietary intake. These results demonstrate, in a trial setting, changes in metabolite profile from manipulation of dietary macronutrient content to lower BP levels. However, the metabolite profile in relation to micronutrients such as dietary sodium intake remains unknown.

The study aims are (1) to examine the associations of urine metabolites with urinary sodium levels and BP control; (2a) to determine the feasibility and preliminary efficacy of delivering an SRD intervention focused on changes in metabolomic profiling and reduction of urinary sodium level and BP; (2b) to estimate the effect size of the SRD intervention on metabolomic profiling, urinary sodium level, and BP metrics and (3) to examine the association of the SS candidate gene with urine metabolites, sodium excretion, and BP control.

The study results will increase knowledge regarding how the SRD alters the urinary metabolome in pre-hypertensive patients, investigating associations of salt sensitivity and within- and between-person variations in the SRD intervention, and exploring how these alterations may improve BP control and cardiovascular health. Also, it will provide foundational information for future work on developing personalized nutrition interventions to reduce dietary sodium intake through identified mechanisms.

3. Objectives and Endpoints *All data points collected in the study should support an objective or have a regulatory purpose.* *Complete the table – add rows as needed.*

3.1. Objective(s) Clearly and concisely define the primary and secondary outcomes.	3.2. Endpoint Clearly define the endpoints. (endpoints are the basis for concluding that the objective has been met).	3.3. Justification for Endpoint Briefly explain why the endpoint(s) were chosen.

 To examine the associations of urine metabolites with urinary sodium levels and BP control. 	
 The metabolite profiles identified in this study will provide insight into the mechanisms underlying changes in sodium intake and BP levels in hypertension. 	
 Previous studies in our team found some novel metabolites which are reflecting dietary sodium intake using targeted urinary metabolites.

 To determine the feasibility, preliminary efficacy, and estimate of the effect size of sodium- 	
 Findings of the study will help develop effective interventions to improve sodium restricted 	
 Numerous studies have shown that low-sodium diet can reduce blood pressure and improve cardiovascular outcomes.

restricted diet intervention on changes in metabolomics profiling and BP reduction among 40 pre-hypertensive patients.	diet adherence and cardiovascular outcomes.	

 To examine the association of the salt sensitivity candidate genes with urine metabolites, sodium excretion, and BP control. 	
 Findings of the study will explain how the salt sensitivity moderates the relationships among urine metabolites, sodium excretion, and BP control. 	
 Previous studies found some genetic variants which are relevant to the salt sensitivity, and these genetic variants are highly associated with hypertension.

4. Rationale

Briefly state the reason for conducting the clinical trial.

Hypertension is a major public health concern. However, the effects of a sodium-restricted diet (SRD) on blood pressure vary, and adherence to an SRD is not optimal. In addition, few studies have examined individuals' metabolic responses to the SRD. In a secondary analysis, we further will examine genetic variants associated with salt sensitivity and whether such a genetic component is associated with sodium excretion and BP control.

5. Study Design

5.1. Number of Groups/Arms		2	Group name(s)	Group 1: Modified Sodium Watcher Program + Digital self-monitoring Group 2: Usual care + Digital self-monitoring								

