8.4. Laboratory Tests

Blood test:

A total 4.0ml of peripheral blood will be drawn into two EDTA tube during pre-test. The EDTA tube will be centrifuged at 4,000 rpm +4°C for 10 minutes, then serum will be transferred into an Eppendorf tube and stored at -80°C. The Illumina Infinium system will be used for high-throughput genotyping of single nucleotide polymorphisms (SNPs) using microarrays. Genotyping will be conducted by Biobanking and Genome Analysis Core Laboratory Center.

Urine test:

Each participant will be asked to complete two 24-hour urine collections at baseline and 8-week and the containers and instructions for 24-hour urine collection will be given to participants at the baseline visit. The PI will visit the participant's home to pick up the urine sample at their convenience by following general precautions such as wearing a face mask and social distancing.

[name] for Renal Precision Medicine lab specializes in metabolomics analysis and will use the targeted capillary electrophoresis/mass spectrometry (CE/MS) method for 48 amino metabolites using the 24-hour urinary sample.

Sodium, 24-hour urine with creatinine will be assessed using the 10 mL urine aliquot. The urinary sample will be sent to Quest Diagnostics.

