10.1. Measures to Minimize Bias: Randomization and Blinding

This section should contain a description of randomization and blinding procedures (if applicable to the study design). It should include a description or a table that describes how study participants will be assigned to study groups, without being so specific that blinding or randomization might be compromised. Plans for the maintenance of trial randomization codes and appropriate blinding for the study should be discussed. The timing and procedures for planned and unplanned breaking of randomization codes should be included. Include a statement regarding when unblinding may occur and who may unblind. Provide the criteria for breaking the study blind or participant code. Discuss the circumstances in which the blind would be broken for an individual or for all participants (e.g., for serious adverse events (SAEs)). Indicate to whom the intentional and unintentional breaking of the blind should be reported.

- Subjects (N=40) will be randomized in a 1:1 ratio into two groups using a computer program that generates random numbers to receive modified Sodium Watchers intervention. Everyone will receive a baseline and end of study visits.
- Subjects randomized to (Group 1) intervention group (IG) will be asked to follow the modified Sodium Watchers Program intervention along with goal setting for low salt foods. Each subject will be registered to assign a unique ID in the Connected Health Platform developed by the Center on Smart and Connected Health Technologies at UT Health Science Center San Antonio (UTHSCSA) and each account from the individuals' wireless and wearable devices (Fitbit and BP monitor) will be connected to his or her unique ID through this platform. Subjects will be instructed to log their activities in real-time, including food intake and in-home BP monitoring using Fitbit and accompanied mobile app and BP monitor. Through the Connected Health Platform, the Fitbit app and BP monitor will transmit the data of the intervention group to the research team. The PI will remotely track user engagement and will call participants if they fail to measure any behavior for 3 days using "Sync function" or subscribing to "Alerts" which will alert us when a user has an inactive or invalid status.

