12.3. Populations for Analyses

Clearly identify and describe the analysis datasets (e.g., which participants will be included in each).

For data analysis, we will include data from study participants who have completed baseline and follow-up survey, and anthropometric and biomarker measurements.

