12.4. Statistical Analyses

Include analysis of primary efficacy endpoints, secondary endpoints, safety analyses, and any planned interim analyses

Data analysis will be performed with SAS (Cary, NC) version 9.4 and R (Vienna, Austria) version and 3.6+. After verifying the normality of distribution of the continuous variables, the mean and standard deviations will be calculated. If data are not normally distributed, log transformation will be conducted. All analyses will also be conducted after controlling for age, gender, and BMI.

Specific Aim 1: Using pre-test data, random forest will be applied to identify associations between 48 amino metabolites, BP phenotypes (including SBP or DBP), and 24-hour urinary excretion to predict the classification of study subjects and will be achieved by R program. For urinary metabolites nominated by the random forest analysis, generalized linear model (GLM) will further be performed to generate p values and false discovery rates (FDR) to correct for testing multiple urinary metabolites using the Benjamini-Hochberg procedure.

Specific Aim 2a: Using both pre and post-test data, feasibility will be assessed by measuring: 1) % subjects who come to the 8-week follow-up; 2) number of education sessions attended online (intervention group); 3) % days that subject log his/her meals using mobile dietary app; and, 4) % days that subject log in-home BP using BP monitor device. The preliminary effect of SRD on the outcome variables will be tested by using a repeated measures analysis of variance (RM-ANOVA) with one between-subjects factor (intervention and control) and one within-subject factor (pre-test and post-test).

Specific Aim 2b: We estimate that 20 participants/group will provide sufficient data for estimating intervention effects on metabolomic profiling and reduction of urinary sodium level and BP. The estimated effect size will be used for sample size justification and power analysis for a future larger study.

Specific Aim 3: Using pre-test data, analysis of targeted genotyping will be conducted by the R program. A moderator analysis will be used to determine whether the relationship between urine metabolites or sodium intake and BP depends on the SS candidate gene (GNAI2 SNPs).

All testing will be two-sided and p<0.05 or FDR < 10% will be considered as significant.

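### Aim 1 can leave the team's own earlier sodium-related metabolites untested, because only metabolites nominated by the random forest receive a p value

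*Combined protocol and SAP*

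**What the plan says.** - Section 3.3, first objective, gives one reason for the metabolite endpoint: "Previous studies in our team found some novel metabolites which are reflecting dietary sodium intake using targeted urinary metabolites". It gives no names, number, effect size or direction.
- Section 2 (Background) says that "the metabolite profile in relation to micronutrients such as dietary sodium intake remains unknown".
- Section 8.4 specifies a targeted "method for 48 amino metabolites using the 24-hour urinary sample". The members of the panel are not listed.
- Section 12.4, Specific Aim 1, begins: "Using pre-test data, random forest will be applied to identify associations between 48 amino metabolites, BP phenotypes", together with 24-hour urinary excretion. It continues: "For urinary metabolites nominated by the random forest analysis, generalized linear model (GLM) will further be performed to generate p values", with Benjamini-Hochberg false discovery rates (FDR). No nomination rule is stated, and no metabolite is exempt from nomination.
- Section 12.4 also sets adjustment for age, gender and BMI, two-sided tests, and significance at p<0.05 or FDR below 10%.
- Section 10.1 gives the size: "Subjects (N=40) will be randomized in a 1:1 ratio into two groups". Section 12.3 restricts analysis to completers ("we will include data from study participants who have completed baseline and follow-up survey"), so Aim 1 has at most 40 people.
- Section 12.1 has two hypotheses, on sodium excretion and BP control. Neither concerns metabolites.

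**The concern.** The evidence offered for the endpoint is a set of metabolites already linked to sodium intake, yet the analysis has no place for that set. All 48 metabolites enter the forest on equal terms, and a low rank ends the matter in Aim 1: no estimate, no p value, no FDR. If an earlier metabolite is absent from the results, the reader cannot tell whether it was tested and failed or was never tested. A later study that draws on this pilot for its choice of metabolites would inherit that ambiguity.

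Nominated metabolites have a second problem. They are selected and tested on the same data, and the correction covers only the nominated set. For metabolites with prior support this is avoidable, because they can be chosen without looking at the trial data.

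**Working it through.** **Plan's own figure.** The sample size of 40 comes with no effect size, SD or target power, so there is nothing to reproduce.

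**Inputs from the documents.** n = 40 (upper limit), 48 metabolites, 3 covariates, Benjamini-Hochberg (BH) at 10%, two-sided tests.

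**Assumptions (not in the documents).** Partial correlation with sodium r = 0.30 to 0.50; 6 earlier metabolites on the panel, 3 of them truly related; top 5 or top 10 nominated; independent metabolites.

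**Step 1: one pre-named metabolite at alpha 0.05.** Power = Φ(atanh(r)·√(n − 3 − 3) − 1.96), with √34 = 5.831.
- r = 0.30: Φ(1.805 − 1.96) = 44%
- r = 0.40: Φ(2.470 − 1.96) = 70%
- r = 0.50: Φ(3.203 − 1.96) = 89%

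**Step 2: the correction family.** The strictest BH step is 0.10/m: 0.020 for 5 nominated, 0.010 for 10 nominated, 0.0167 for 6 named. The multiplicity penalty is thus similar on both routes. The relevant comparison is nominated set against named set, since the plan does not correct over all 48.

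**Step 3: missed nominations.** Simulated forest, 3 true metabolites, 400 runs per setting. The range runs from top 10 to top 5 nominated.

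| r | Forest on continuous sodium | Forest on median-split class |
|---|---|---|
| 0.30 | 40–56% | 51–67% |
| 0.40 | 22–35% | 34–50% |
| 0.50 | 7–17% | 19–33% |

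**Step 4: power per true metabolite (BH 10%).** The nomination columns use 3 true metabolites. The direct column tests 6 named metabolites, 3 of them true.

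| r | Nomination, continuous | Nomination, class | Direct |
|---|---|---|---|
| 0.30 | 35–36% | 23–25% | 36% |
| 0.40 | 60–62% | 44–49% | 66% |
| 0.45 | 74–75% | not run | 80% |
| 0.50 | 82–86% | 65–74% | 89% |

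The r = 0.45 row is from a 300-run forest simulation, which gave 61% against 66% at r = 0.40. A simpler noisy ranking in place of the forest gave 55–60% against 67% at r = 0.40.

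Gains at r = 0.40 on continuous sodium: 66 − 61 = 5 points with the 300-run forest; 67 − 60 = 7 to 67 − 55 = 12 with the noisy ranking. At r = 0.45: 80 − 75 = 5 to 80 − 74 = 6. With a class outcome at r = 0.40: 66 − 49 = 17 to 66 − 44 = 22. At r = 0.30 on continuous sodium the power gain is essentially nil.

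Simulation error with 300 runs is at most √(0.25/300) = 2.9 points per figure, so the low end of the gain is small and imprecise.

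**Step 5: a shorter, better list.** If 3 metabolites are named and all 3 are true, direct power is 49%, 77% and 94% at r = 0.30, 0.40 and 0.50. The gain over nomination is then about 8–16 points (continuous) or 20–33 points (class).

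**Step 6: error control.** With no true association, BH within the nominated set still gives at least one discovery in 47–66% of runs (continuous) or 38–50% (class), against a nominal 10%. The power under nomination in Step 4 is therefore obtained without the stated FDR control.

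**The case against.** The plan has fair defences.

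- **It is a pilot.** Section 12.2 calls the study underpowered and confines quantitative results to pilot use. That limits the harm. It does not remove it, because Section 12.4 still declares significance and the results are meant to guide later work.
- **The stated objective is to examine associations, and a whole-panel screen fits that.** This stands. Direct testing of named metabolites would be added to the screen and would not replace it.
- **A strong marker would usually be nominated.** True: at r = 0.50 on continuous sodium, 83–93% of true metabolites are.
- **The two statements on prior knowledge may be compatible.** Section 2 may describe the wider literature, and some metabolites are not a profile. They still need reconciling, because a reader cannot tell how much is already known.
- **The earlier metabolites may not be on the panel.** The documents do not say. The figures of 6 to 10 in Section 2 count metabolites associated with BP in dietary-pattern studies, so they do not supply the number either.

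A reader might also infer more than the documents support:

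- **That power is halved, from about 34% to 66% at r = 0.40.** The 34% comes from BH over all 48, which is not the plan. Missed nominations do not push power below it either: the nomination route gives 55–61% on continuous sodium.
- **That these metabolites are the study's best-supported hypotheses and are wasted.** Section 3.3 cites many studies for the effect of low sodium on BP, and Section 12.1 has no metabolite hypothesis.
- **That the restriction runs through the whole study.** It is written for Aim 1. Aims 2a and 3 state no nomination step, although they do not list their metabolite variables.

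**Conclusion.** The point holds for Aim 1, at modest size. As written, a metabolite of the kind cited to justify the endpoint can finish Aim 1 with no test, and nothing in Section 12.4 prevents this.

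Under the 6-candidate, 3-true assumptions, a true metabolite misses nomination in roughly 20–40% of runs at r = 0.40, and less often as r rises. Direct testing adds about 5–12 points of power for r of 0.40 to 0.45, and more if the forest predicts a class, which the Aim 1 wording allows. These figures depend on the assumed correlation, number of candidates, nomination count and independence between metabolites.

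The firmer reasons for the change do not depend on those assumptions: every named metabolite gets a p value, and none is both selected and tested on the same data.

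**What to change.** In Section 12.4, Aim 1:

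1. Before analysis, list by name the earlier sodium-related metabolites that are on the 48-metabolite panel.
2. Test all of them in the adjusted GLM against 24-hour urinary sodium, whatever their forest rank, as a separate pre-specified family with Benjamini-Hochberg at 10%.
3. Label the forest screen of the remaining metabolites, and the tests that follow from it, exploratory.

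If none of the earlier metabolites is on the panel, correct the justification in Section 3.3, since it would not support this assay. In either case, reconcile the statement on unknown profiles in Section 2 with Section 3.3.

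The cost is a short list and a few sentences, with no new data, visits or participants. The one statistical downside is that the 10% FDR then holds within each family and not jointly.

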5.2. Overall Design Select all applicable												
	Randomization				Cluster Randomized							
	Group-Sequential				Adaptive Design							
	Parallel Design				Placebo-Controlled							
	Superiority				Equivalence		 Non-inferiority					
Device		Pilot			Pivotal		 Post-Approval					
Drug/Biologic		Phase 1		Phase 1/2		Phase 2		Phase 2/3		Phase 3		Phase 4
	Dose escalation		If yes, details →									
	Dose ranging		If yes, details →									
	Sub-studies		If yes, details →									

5.3. Other Design Details: This will be an 8-week randomized controlled trial. The study will start after the IRB approval from UT Health San Antonio. Subjects recruitment will be performed in the communities and utilized EHR (Electronic Health Record) and data collection will be conducted at UT Health San Antonio School of Nursing. Bio-specimen (blood sample) will be transported to and processed in the laboratories of Center for Renal Precision Medicine and School of Nursing at UTHSCSA.

6. Study Population

6.1. Study Population(s) Label/Name	6.2. Identify the criteria for inclusion The criteria that every potential participant must satisfy, to qualify for study entry.	6.3. Identify the criteria for exclusion The characteristics that make an individual ineligible for study participation.
To add more populations – select a row, copy & paste	All individuals in this study population must meet all of the inclusion criteria in order to be eligible to participate in the study	All individuals in this study population meeting any of the exclusion criteria at baseline will be excluded from study participation.
• 40 Pre-hypertensive patients	
 Aged 40 or older. Systolic blood pressure of 120-159 mmHg or diastolic blood pressure of 80-99 mmHg, whether or not taking blood pressure medications. 	
 Participating in another related research study Cardiovascular disease event (e.g. stroke, myocardial infarction) in prior 6 months

	
 Smartphone with a data plan Valid email address Willing and able to participate in online study videoconferencing visits (Zoom) Reads and writes in English 	
 Active cancer Recent hospitalization due to psychiatric condition or event Pregnancy or breastfeeding - current or planned during the study period Documented dementia Prisoners Diabetes Diagnosis Heart Failure Diagnosis
6.4. Will screen failures be allowed to re-screen at a later date?	 No  Yes	If yes, describe criteria below ↓

7. Study Intervention(s) being tested or evaluated

This can include prevention, diagnostic or therapeutic interventions (e.g., drug or device) or educational, health services or basic science interventions (e.g., educational program, health care delivery model, or examining basic physiology)

- Modified Sodium Watchers Intervention Group (IG): The modified Sodium Watchers Program intervention consists of 8 weeks of education sessions (45 minutes) for gradual reduction to low salt foods that will be held at the subjects' preferred time delivered to their homes using Zoom which is a video conferencing program through the subject's personal computer or smartphone. In addition, goal setting for SRD and digital self-monitoring using Fitbit and its companion app, and wireless BP monitor will be used over 8 weeks.
 - Understanding hypertension
 - Low sodium diet in hypertension
 - Keeping a food diary
 - Taking a blood pressure
 - Identify barriers in following low sodium diet
 - Strategies to overcome barriers
- Usual Care Control Group (CG): The 20 subjects will receive their routine medical and nursing care for pre-hypertension that consists of a recommendation to follow SRD and take medications as prescribed. Usual care consists of recommendations to follow an SRD, but without explicit skills training including instructions on gradual adaptation to sodium restricted diet, follow-up of progress or provision of monitoring. In addition, digital self-monitoring using Fitbit and its companion app, and wireless BP monitor will be used over 8 weeks.

8. Protocol-Directed procedures, items, services or tests

List all procedures directed by the study plan - including items or services provided as part of routine or conventional care and those needed to diagnosis or treat research related complications.

Important Note – The protocol directed procedures listed must match those in the [Schedule of Activities \(attachment\)](#)

